## 1.0 Objectives:

### 1.1 Specific Aims and hypotheses are to:

**Aim 1:** Test the effectiveness of the TAKE IT strategy, compared to usual care, to improve kidney transplant (KT) recipients’:

**H1:** treatment knowledge (indications, potential side effects, demonstrated proper use)

**H2:** medication use (regimen adherence via self-report, pill count, tacrolimus levels)

**H3:** transplant-specific outcomes ( $\Delta$  eGFR, quality of life, re-hospitalization)

**H4:** chronic disease outcomes (blood pressure, HbA1c)

**Aim 2:** Examine the persistence of any effects of the TAKE IT strategy on outcomes over 2 years among new and established KT recipients.

**Aim 3:** Evaluate the fidelity of each component of the TAKE IT strategy over time, and investigate any patient, provider, or transplant center barriers to implementation.

**Aim 4:** Determine the costs of delivering the TAKE IT strategy from a transplant center perspective.

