likelihood estimation will be used to create a composite adherence metric by generating a single factor score from the 5 measures of adherence.

**Regimen Knowledge:** Patient identification of drug names and indication will be assessed via assessments used previously by [name] and colleagues (ref). Patients will be asked about each of these via structured, open-ended items. Understanding of proper dosing will be assessed using the 24 hour recall task described above, but patients will be given credit if they demonstrate knowledge of how to take their medication correctly regardless of their actual behavior. From this assessment, we can also determine how patients are taking their entire multi-drug regimen, and if medications are consolidated in the most efficient manner. We will examine the total number of times throughout a 24 hour period patients indicate they will take medicine.

**Quality of Life.** We will use Patient Reported Outcomes Measurement Information System (PROMIS) Physical Function, Anxiety, Depression and Global Health subscales.

**Clinical Outcomes.** will be collected via EHR by site. Transplant-specific outcomes include: 1) change in estimated glomerular filtration rate (eGFR; ml/mn) over 24 months, 2) *Re-hospitalization*: Acute care hospitalizations 3) *Acute Rejection*: proven biopsy meeting organ-specific Banff criteria; 4) *Toxicity*: related to CNI medications (hypertension; neuro-toxic events); 5) *Infection*: CMV, BKV, bacterial infections assessed by laboratory tests and/or biopsies. *Blood pressure* (continuous SBP; control (y/n): SBP<140 & DBP<90) and *glycemic control (HbA1c)* will also be examined in those with hypertension and diabetes.

[figure not shown]

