**11.0 Data and Specimen Management:**

**11.1 Analysis Plan.**

All analyses will be performed in SAS v9.4 (SAS Institute, Cary, NC). [name] will perform analyses under the direct supervision of Drs. [name], [name] and [name]. Drs. [name] and [name] will also provide guidance.

Aim 1.

The proposed trial uses a 1:1 randomized design that assigns patients to TAKE IT or usual care within each cohort. We will accrue approximately 700 patients (350 de novo, 350 established) anticipating 90% retention in the de novo cohort (85% established) for follow-up at 1 year, leaving a minimum 525 patients for primary analyses. High retention will be supported through close follow-up, mailed reminders, birthday cards, and a newsletter. Given the clinical follow-up necessary for KT recipients, we are confident we will achieve this goal.

Regimen adherence at one year is the primary outcome of interest for Aim 1, with Rx knowledge and individual adherence measures also of primary interest. Secondary outcomes include quality of life (PROMIS outcomes and FKSI) and the clinical outcomes of change in eGFR, and any transplant-related re-hospitalization. Blood pressure control in those taking anti-hypertensive medications will also be examined. Relationships between

adherence and potential confounders (age, comorbidity, cognitive ability, regimen complexity, internet use, dose of intervention, etc.) will also be examined. For all outcomes, we will use generalized linear models (GLMs), adjusted for confounders and study site, specifying the logit link function for binary outcomes and identity link for continuous outcomes (quality of life, change in eGFR, SBP). Treatment group will be the independent variable of primary interest, with usual care specified as reference group. We will also include time since transplant at baseline (in months), baseline value of the outcome, and any potential confounding covariates noted in bivariate analysis. For outcomes measured per medication, a generalized estimating equation (GEE) approach will be employed to adjust standard errors for within-patient correlation. Should TAKE IT have an effect on outcomes, secondary analyses will examine if any of the potential confounders considered exhibit any effect modification.

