### Aim 2.

Generalized linear mixed models (GLMMs) will be used to examine intervention effects over the course of the study. Link functions will be included as described above for the GLM models. Adherence concerns may differ in the two cohorts, thus separate models will be employed for each cohort (de novo, established). Treatment group will be the independent variable of primary interest, modeled as a fixed effect with the usual care group specified as reference group. We will also include fixed effects for site (NU, Mayo), time since transplant (in months), and potential confounding covariates noted in bivariate analyses. Random participant effects for each participant will be included to account for repeated measurements nested within each participant (assuming a compound symmetry, although we will fit autoregressive structures as well, comparing fit using AIC and BIC criterion). Outcomes recorded at each interview will be analyzed by visit whereas adherence measured by tacrolimus levels, along with blood pressure control will be analyzed in 6-month intervals as described above. A time-since-transplant-by-arm interaction term will be included to examine if outcome trajectories/slopes over time differ by study arm. Since prescription knowledge and adherence will be assessed for each medication, 2-level GLMM will be used for these outcomes with medications nested in participants. For  $\Delta$  eGFR and re-hospitalization outcomes, GLM models will be used since outcomes over 2 years are summarized in a single measurement. In the de novo cohort, change in eGFR from transplant to 2 years post-transplant and # hospitalizations (any hospitalization, if rare) within 2 years post-transplant will be modeled. For the established cohort, the time period for the both measures will span from transplant to 2-year study visit. It is possible those who do not complete the 2-year visit will differ in important characteristics (e.g. cognition, comorbidity), which could bias results. We will use collected data at prior interviews to understand the extent that individuals who complete follow-up differ from those who do not. If differences are found, pattern-mixture models will be employed by classifying participants' drop-out type or pattern (e.g. completed, refused, lost to follow up, death). This variable will then be added to mixed effects models to account for differences.

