*Exploratory Analyses.* A single measurement for each exploratory transplant related clinical outcome (i.e. acute rejection, toxicity, infection) will be modeled at the end of the study indicating the total number of occurrences (or any for rare outcomes) over the course of the study using GLM models as described above. We recognize we likely will not have sufficient power to find differences in these outcomes. Intervention effects on blood pressure and glycemic control will be examined among those with diabetes and/or hypertension.

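### Aim 2 counts established-cohort hospitalisations and eGFR change from transplant, up to 24 months before randomisation, which lowers power for hospitalisations and may lower precision for eGFR

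*Combined protocol and SAP*

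**What the plan says.** Section 11.1, Aim 2, analyses change in eGFR and re-hospitalisation with one summary value per patient: "GLM models will be used since outcomes over 2 years are summarized in a single measurement". The window differs by cohort.

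- De novo: "change in eGFR from transplant to 2 years post-transplant and # hospitalizations (any hospitalization, if rare) within 2 years post-transplant".
- Established: "For the established cohort, the time period for the both measures will span from transplant to 2-year study visit".

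Sections 3.2 and 9.7 enrol and randomise patients between 5 weeks and 24 months after transplant.

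Other parts of the plan describe different windows. Section 1.1 frames Aim 2 as the "persistence of any effects of the TAKE IT strategy on outcomes over 2 years among new and established KT recipients". Section 8.4 defines the renal outcome as "change in estimated glomerular filtration rate (eGFR; ml/mn) over 24 months". The exploratory clinical outcomes are each patient's "total number of occurrences (or any for rare outcomes) over the course of the study".

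On covariates, the Aim 1 text says "We will also include time since transplant at baseline (in months), baseline value of the outcome". Aim 2 lists site, time since transplant and confounders found in bivariate analyses. It does not repeat the baseline-value term. The only links named, in Aim 1 and carried into Aim 2, are logit for binary and identity for continuous outcomes.

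**The concern.** For an established patient the counted period can reach 48 months, of which up to 24 come before allocation. Hospitalisations in that earlier part have the same expectation in both arms. On a ratio scale they pull the estimate toward 1. On a difference scale they leave the estimate unbiased and add variance. In the any-hospitalisation form, a patient already admitted before randomisation can no longer show a benefit. In every form a real benefit is harder to detect.

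For eGFR, the starting value at transplant is balanced by randomisation, so the expected between-arm difference does not change. Precision may fall, depending on how strongly eGFR at transplant and at randomisation each correlate with the final value, and on whether a baseline term is used.

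These are the transplant-specific outcomes of hypothesis H3, and Aim 2 models each cohort separately. A diluted result in the established cohort could be read as no lasting effect.

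**Working it through.** **Inputs.** From Table 5, established cohort: 170 per arm; re-hospitalisation 47% under usual care with minimum difference 14.8 points (so 32.2%); eGFR change SD 15.0 with minimum difference 4.6. Alpha is 5%, taken as two-sided. Table 5 is headed 1 year, with a 2-year footnote for eGFR only, so I treat the re-hospitalisation risks both as 24-month and as 12-month risks. Assumed, because the documents give no values: a constant hospitalisation rate, the pre-randomisation time, and dispersion k of 0 or 0.5.

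**Reproducing the plan.** Two proportions with pooled variance, 47% versus 32.2%, 170 per arm: power 79.95%. Two means, SD 15: (1.96 + 0.842) × 15 × √(2/170) = 4.56, which matches 4.6.

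**Hospitalisation counts.** Monthly rates are h0 = −ln(1 − 0.47)/T and h1 = −ln(1 − 0.322)/T, with T = 24 or 12. Their ratio is 0.612. With `pre` months before randomisation, the expected counts are m0 = h0 × (24 + pre) and m1 = h0 × pre + h1 × 24. The log-ratio Wald test has SE = √[(1/m0 + k)/n + (1/m1 + k)/n].

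Worked case, T = 24, pre = 12, k = 0, n = 170: m0 = 0.952, m1 = 0.706, ratio 0.741, SE 0.1205, power 70%. With pre = 0 the means are 0.635 and 0.389, SE 0.1562, power 88%.

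| Pre-randomisation months | Observed ratio | T=24, k=0 | T=24, k=0.5 | T=12, k=0 | T=12, k=0.5 |
|---|---|---|---|---|---|
| 0 | 0.61 | 88% | 81% | 99% | 96% |
| 6 | 0.69 | 79% | 67% | 97% | 86% |
| 12 | 0.74 | 70% | 55% | 94% | 74% |
| 15 | 0.76 | 66% | 51% | 92% | 69% |
| 24 (bound) | 0.81 | 56% | 39% | 85% | 54% |

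An identity link gives almost the same power (T=24, k=0: 89% at 0 months, 70% at 12). The Aim 1 text expects 85% retention of 350 established patients, which is 350 × 0.85 / 2 = 148.75 per arm. At 149 per arm the 12-month values are 64% and 50% (T=24), or 91% and 69% (T=12).

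**Does the time-since-transplant covariate repair this?** I simulated 3,000 trials per setting with entry spread evenly from 5 weeks to 24 months (mean 12.6), gamma frailty, and that covariate in the model. Power, counting from randomisation and then from transplant, at 170 per arm:

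- T=24: 90% to 71% (k=0); 81% to 54% (k=0.5).
- T=12: 99% to 94% (k=0); 95% to 74% (k=0.5).

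The covariate accounts for window length but does not remove the earlier events. Rejection under the null was 5.4% to 5.8% (Monte Carlo SE 0.4 points).

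**Any-hospitalisation form.** Let q be the share already admitted before randomisation, independent of later admission. The arm risks become q + (1 − q) × 0.47 and q + (1 − q) × 0.322. With a constant rate on the 24-month reading, q = 0.147, 0.272 and 0.470 at 6, 12 and 24 months. Power falls from 80% to 64.5%, 51.7% and 34.0%. At 12 months the risks compared are 61.4% and 50.6%.

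**De novo.** If Mayo's 6-week definition in Section 5.2 applies at both sites, about 1.15 to 1.4 months precede randomisation. Poisson power (32% versus 17.4%, 135 per arm) goes from 83% to 78–79% (T=24), or from 98% to 97% (T=12). Part of this drop is lost follow-up, because that window ends 2 years after transplant: truncation alone takes 83% to 81%.

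**eGFR.** If the SD does not grow with the window, the detectable difference stays at 4.6. If variance grows in proportion to the window and no baseline term is used, SD = 15 × √((24 + pre)/24), and the detectable difference is 5.1, 5.6, 5.8 and 6.4 at 6, 12, 15 and 24 months.

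**The case against.** The strongest reply is that the consequence is limited. These are secondary outcomes; the primary is adherence at 1 year. Neither arm is favoured and type I error holds. Aim 1 also lists re-hospitalisation and eGFR change, with no window stated, so Aim 2 may not be the only test. All of this stands, and it limits the severity.

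The plan also states no power for these Aim 2 outcomes. The count calculations convert Table 5's percentages to rates, so most start above the plan's 80%, and the loss depends on assumed rates, dispersion and entry times. On the 1-year Poisson reading, power stays at about 85% even at the bound. This stands for the size but not for the direction. The binary form, which does start from the plan's 80%, loses more.

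On eGFR, Aim 1's baseline-value term sits in a specification for all outcomes, and carry-over to Aim 2 is plausible. That is fair: the eGFR point is mainly a request to say so. For a hospitalisation count, no baseline value is defined anywhere, so carry-over would not settle that part.

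The unnamed count model and the Table 5 time labels are separate matters of missing detail. They add no weight to the window problem but are easily settled with it.

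**Conclusion.** The concern holds and should be fixed. As written, the established-cohort window includes up to 24 months that the intervention cannot influence, and it disagrees with the plan's own two-year and study-period descriptions. That part needs no assumption.

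For hospitalisations the power loss is certain in direction and uncertain in size. At about 12 pre-randomisation months with 170 per arm, it runs from 5 points (1-year reading, Poisson: 99% to 94%) to 28 points (24-month reading, any hospitalisation: 80% to 52%). For eGFR the estimate is unbiased; precision may be unchanged or may worsen, with a detectable difference between 4.6 and a bound of 6.4. The de novo version is small.

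The sample sizes used reflect 1-year retention. Two-year retention is not given, so absolute power at 24 months could be lower under either window.

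**What to change.** In Section 11.1, Aim 2, start both outcomes at randomisation and end them at the 24-month study visit, in both cohorts.

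- **eGFR:** analyse with the value at randomisation as covariate, and state that Aim 1's baseline-value term applies to Aim 2.
- **Hospitalisations:** count from randomisation in a named count model, for example negative binomial, with log follow-up time as offset. Include the number of pre-randomisation hospitalisations and months since transplant at baseline as covariates. Use the same window if the any-hospitalisation form is adopted.
- **Table 5:** state the time window for the eGFR and re-hospitalisation rows so that they match the analysis.

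The cost is SAP wording only, because Section 8.4 already collects the clinical outcomes from the EHR. Fewer events are counted per patient, but the events dropped are those the intervention could not have changed.

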*Power Calculation.* The sample size calculation was based on the availability of 700 transplant patients estimated by the number of transplants conducted in 2012-2014 across the two sites. With the sample size set at 610 accounting for 85-90% retention at 1 year, we present the minimum differences we will be able to detect between the intervention and usual care arms for each outcome of interest. For the main outcome of medication adherence, we estimate 45% of the sample to be non-adherent using the composite score described above taking estimates for each individual measure into account. We will have sufficient power ( $\geq 80\%$ ) to detect differences of 11% in the entire sample assuming a 5% Type I error rate. Should TAKE IT be associated with potential confounders, calculations show that an R-squared of 0.2 between predictors (a conservatively high estimate under randomization), we would still maintain 70% power to detect the 11% difference. Although adjusting for confounders would decrease variability in adherence, and increase power. Detectable differences for individual adherence measures along with estimates and effect sizes for other outcomes of interest are listed in Table 5.

Table 5. Detectable Differences in Health Outcomes between Study Arms at 1 Year

Outcome	Total (n=610) 305/arm		De Novo (n=270) 135/arm		Established (n=340) 170/arm	
	Usual Care Estimate	Minimum Difference	Usual Care Estimate	Minimum Difference	Usual Care Estimate	Minimum Difference
Primary Outcomes						
Rx Knowledge, %	50	11.3	60	15.9	45	15.1
Rx Non-adherence, %	45	11.0	35	15.2	50	15.0
Self-report, %	35	10.3	29	14.1	44	14.6
Objective (pill count), %	45	11.1	35	11.3	50	15.0
Claims (PDC), %	30	9.8	23	12.7	38	14.0
Biologic (SD Tacrolimus), %	40	10.8	30	14.3	45	14.7
Secondary Outcomes						
Quality of life, mean(SD)	46.2 (9.0)	2.0	45.8 (7.2)	2.5	49.5 (9.0)	2.7
Clinical outcomes						
$\Delta$ eGFR, mean(SD)*	-5.8 (9.0)	2.9	-3.0 (11.0)	3.8	-8.0 (15.0)	4.6
Re-hospitalizations, %	40	10.8	32	14.6	47	14.8
Systolic BP, mean(SD)**	136.7 (8.3)	2.2	138.3 (12.9)	5.1	135.0 (7.9)	2.8

\* $\Delta$  eGFR estimates over 2 years

[figure not shown]
\*\*estimate 75% of cohort has hypertension (Total: n=458, 229/arm; De Novo: n=202, 101/arm; Established: n=256, 128/arm)

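### Table 5 sizes the 2-year eGFR change on the numbers retained at 1 year, with no allowance for second-year loss

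*Combined protocol and SAP*

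**What the plan says.** Section 11.1, Power Calculation, sets the sample "With the sample size set at 610 accounting for 85-90% retention at 1 year". Table 5 is titled "Detectable Differences in Health Outcomes between Study Arms at 1 Year", and its columns carry the matching counts, for example "Established (n=340) 170/arm"; the de novo column has 270 patients, 135 per arm. The eGFR row sits in the same columns, but its footnote reads "eGFR estimates over 2 years".

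The Aim 2 text in Section 11.1 treats eGFR change and re-hospitalization differently from the repeated measures: "GLM models will be used since outcomes over 2 years are summarized in a single measurement". For eGFR, the window ends 2 years after transplant in the de novo cohort and at the 2-year study visit in the established cohort. The same text recognises attrition by then: "It is possible those who do not complete the 2-year visit will differ in important characteristics".

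The only retention figures are in the Aim 1 text: 90% de novo and 85% established, both at 1 year. No 2-year figure is given. Section 8.4 says that clinical outcomes come from the electronic health record (EHR).

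**The concern.** A detectable difference should rest on the number of patients who will have the outcome at the time it is measured. Here the time point is 2 years and the number belongs to 1 year. In the GLM as specified, a patient without a 2-year eGFR contributes nothing. The pattern-mixture remedy in Aim 2 is attached to the mixed models, so it does not restore this sample.

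Change in eGFR is the graft-function outcome named under H3 and is listed as secondary in Aim 1. If the 2-year sample is smaller than Table 5 assumes, a null result would be read against a sensitivity that the analysis does not have.

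**Working it through.** **Inputs.** All are from Section 11.1. Type I error is 5% ("assuming a 5% Type I error rate"), with sidedness not stated. Power of at least 80% is stated for adherence and taken here to apply to the whole table. Established: 170 per arm, SD 15.0, printed difference 4.6. De novo: 135 per arm, SD 11.0, printed difference 3.8. Total: 305 per arm, SD 9.0, printed difference 2.9.

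**Formulas** (two-sample means, normal approximation, n per arm):

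- Detectable difference = (1.960 + 0.842) × SD × √(2/n)
- Power at difference d = Φ(d / [SD × √(2/n)] − 1.960)

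**Step 1: reproduce the printed cohort cells.**

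- Established: 2.802 × 15 × √(2/170) = 4.56, printed 4.6. Power at 4.6 = 80.7%.
- De novo: 2.802 × 11 × √(2/135) = 3.75, printed 3.8. Power at 3.8 = 81.0%.
- One-sided testing would give about 4.05 and 3.33, which do not match, so the table is two-sided.

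Both cells therefore use the 1-year counts with nothing removed for year 2. They have little slack: 80% power needs 167 per arm for 4.6 and 132 per arm for 3.8.

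**Step 2: apply a range of second-year retention.** The percentage is the share of the 1-year sample that has a 2-year eGFR. It is an assumption, because the plan gives no figure.

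| Share with 2-year eGFR | Established n/arm | Power at 4.6 | Detectable | De novo n/arm | Power at 3.8 | Detectable |
|---|---|---|---|---|---|---|
| 100% | 170 | 80.7% | 4.56 | 135 | 81.0% | 3.75 |
| 95% | 161.5 | 78.7% | 4.68 | 128.25 | 79.0% | 3.85 |
| 90% | 153 | 76.5% | 4.80 | 121.5 | 76.8% | 3.95 |
| 85% | 144.5 | 74.1% | 4.94 | 114.75 | 74.4% | 4.07 |
| 80% | 136 | 71.5% | 5.10 | 108 | 71.9% | 4.19 |

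Repeating each cohort's first-year rate corresponds to the 85% line for established and the 90% line for de novo. The detectable differences then grow by factors of 1/√0.85 = 1.085 and 1/√0.90 = 1.054.

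**Step 3: cohort sizes.** Table 5 implies enrolment of 270/0.90 = 300 de novo and 340/0.85 = 400 established. Aim 1 states 350 and 350. On 350/350 with the first-year rates repeated:

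- Established: 350 × 0.85 = 297.5 at 1 year (148.75 per arm), power at 4.6 = 75.3% before any second-year loss. After it, 126.4 per arm and 68.4%.
- De novo: 350 × 0.90 × 0.90 = 283.5 at 2 years, above the 270 in Table 5. Power at 3.8 is about 83% and the detectable difference about 3.66, so there is no shortfall.

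**Step 4: the Total cell.** 2.802 × 9.0 × √(2/305) = 2.04, not the printed 2.9. With SD 9.0, power at 2.9 is 97.8% at 305 per arm and still about 96% at 266 per arm (121.5 + 144.5). The printed 2.9 would need an SD of about 12.8. This cell cannot show the effect of second-year loss until its two figures agree.

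**The case against.** The strongest reply is that eGFR is a laboratory value from the EHR, not an interview answer. Section 9.11 describes monthly labs after the early months, Section 7.2 puts the 24-month interview on the phone, and Section 25.3 provides authorization for record review. Under Section 13.1 a patient is withdrawn only when unresponsive 6 months past an interview's due date. Someone present at 12 months who first misses the 18-month interview reaches that point at month 24, when the established window closes. A de novo patient enrolled at 6 weeks (the Mayo description in Section 5.2) reaches 2 years post-transplant about 22.5 months after enrolment, before that. So a missed interview need not remove the eGFR.

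This stands, and it means that interview retention probably overstates the loss of eGFR. It does not close the gap. Death, active withdrawal and transfer of care can still remove the value. Aim 2 itself lists death and refusal among its drop-out patterns, and Section 13.2 speaks only of data collected up to withdrawal. The plan quantifies none of this.

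It is also fair that the sample was set by patient availability, that Table 5 lists detectable differences and not target effects, and that the outcome is secondary. These limit the importance of the point but do not make the row correct.

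**Conclusion.** The point holds as a minor one: the eGFR row reports 2-year detectable differences on 1-year numbers, with no allowance for loss in the second year.

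Its size depends on an availability figure that the plan does not give. Over 100% to 80% of the 1-year sample, established power at 4.6 runs from 80.7% to 71.5% and the detectable difference from 4.56 to 5.10. These figures take Table 5's cohort sizes and SDs as printed. The 1-year primary outcome is unaffected.

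Three stronger readings are tempting, and the documents do not support them:

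- **Established power falls to 74% under the plan's own loss rate.** The plan states retention at 1 year only. The 74% needs a further 15% loss of eGFR values, which is an assumption.
- **Pooled power falls from 80% to 74%.** At the printed SD and difference it stays above 95%. That fall appears only if an SD of about 12.8 replaces the printed 9.0.
- **Enrolment of 350/350 makes matters worse throughout.** It lowers the established number but leaves the de novo cohort without a shortfall. Much of the established drop (80.7% to 75.3%) comes from the cohort-size discrepancy and not from second-year loss.

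**What to change.** 1. Label the eGFR row of Table 5 as a 2-year outcome.
2. State the expected 24-month eGFR availability for each cohort, allowing for EHR capture, withdrawal and death, and say whether eGFR continues to be collected from the record after a patient is lost to interview.
3. Reconcile the cohort sizes in Aim 1 (350/350) with those implied by Table 5 (300/400), then recompute the cohort detectable differences on the 2-year numbers. For orientation, at 300/400 and a repeat of the first-year rates they would be about 3.95 de novo and 4.94 established.
4. Recompute the Total cell only after its SD of 9.0 and difference of 2.9 have been reconciled.
5. While editing, confirm whether the re-hospitalization row is meant at 1 year, as the table title says, or over 2 years, as Aim 2 analyses it.

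The cost is one table row and a sentence on availability. No design element changes. The cohort figures become about 5% (de novo) to 8% (established) less favourable under that illustration, and less so if EHR capture is good.

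### Table 5's three usual-care SDs for systolic BP (8.3 overall, 12.9 and 7.9 by cohort) cannot all hold, so the whole-sample detectable difference of 2.2 mmHg conflicts with the cohort figures beside it

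*Combined protocol and SAP*

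**What the plan says.** In Section 11.1, the Power Calculation introduces Table 5 with the statement that "we present the minimum differences we will be able to detect between the intervention and usual care arms for each outcome of interest". The table is built on the number expected to remain at one year ("With the sample size set at 610 accounting for 85-90% retention at 1 year"). For the main adherence outcome the text attaches at least 80% power, "assuming a 5% Type I error rate".

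The systolic BP row reads, for total, de novo and established in turn: "Systolic BP, mean(SD) 136.7 (8.3) 2.2 138.3 (12.9) 5.1 135.0 (7.9) 2.8". Each group shows a usual-care mean with its SD, then the minimum detectable difference. The footnote restricts this row to patients with hypertension ("estimate 75% of cohort has hypertension") and gives the numbers: "Total: n=458, 229/arm; De Novo: n=202, 101/arm; Established: n=256, 128/arm".

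No derivation or separate source is given for the whole-sample SD of 8.3.

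**The concern.** The total is not a separate population. By the footnote it is the two cohorts added together, overall and within each arm. The variance of a mixture cannot be smaller than the weighted average of its components' variances. An overall SD of 8.3 lies very close to the established cohort's 7.9, although 44% of the patients come from a cohort with SD 12.9.

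Blood pressure is named in hypothesis H4 (Section 1.1), and systolic BP is the only H4 measure with a detectable difference in Table 5. A reader planning or interpreting the BP comparison would take 2.2 mmHg as the difference the whole sample can detect. On the cohort figures in the same row, it cannot do so at the stated power without some reduction in variance that the table does not mention.

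**Working it through.** **Inputs** (Table 5 and its footnote): usual-care mean (SD) 136.7 (8.3) total, 138.3 (12.9) de novo, 135.0 (7.9) established; 229, 101 and 128 per arm. Type I error is 5%. Sidedness is not stated, and 80% power is stated only for adherence, so both are tested in step 1.

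**1. Reproduce the plan's figures.** For two means, detectable difference = (1.960 + 0.842) × SD × √(2/n per arm):

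- Total: 2.802 × 8.3 × √(2/229) = 2.17 (stated 2.2)
- De novo: 2.802 × 12.9 × √(2/101) = 5.09 (stated 5.1)
- Established: 2.802 × 7.9 × √(2/128) = 2.77 (stated 2.8)

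All three reproduce at two-sided 5% and 80% power. For the total, a one-sided test gives 1.93, 90% power gives 2.51, and 305 per arm gives 1.88, so none of these was used. The formula is sound, and 8.3 was the input behind 2.2.

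**2. Whole-sample SD implied by the cohorts.** Weights are 202/458 = 0.441 and 256/458 = 0.559.

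- Within-cohort variance: 0.441 × 12.9² + 0.559 × 7.9² = 73.4 + 34.9 = 108.3, so SD = 10.41
- Between-cohort variance: 0.441 × 0.559 × (138.3 − 135.0)² = 2.7
- Total variance: 111.0, so SD = 10.53

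Rounding does not explain the gap. With the cohort SDs at their lowest before rounding (12.85 and 7.85), the within-cohort SD is √(0.441 × 165.1 + 0.559 × 61.6) = 10.36.

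**3. Mix that would give 8.3.** Ignoring the gap in means, the de novo share would be (8.3² − 7.9²)/(12.9² − 7.9²) = 6.48/104 = 6.2%, against 44% in the footnote. The printed total mean of 136.7 points the other way: (136.7 − 135.0)/3.3 = 52% de novo.

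**4. Consequence if the cohort SDs stand** (229 per arm, unadjusted, two-sided 5%; power = Φ(2.2/SE − 1.96), SE = SD × √(2/229)):

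| Whole-sample SD | Detectable difference at 80% | Power at 2.2 mmHg |
|---|---|---|
| 8.3 (printed) | 2.17 | 81.0% |
| 10.41 (within cohort) | 2.72 | 61.9% |
| 10.53 (with gap in means) | 2.76 | 60.8% |

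Rounding of the 2.2 itself (2.15 to 2.25) moves the power in the last two rows only between about 59% and 64%.

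**5. Effect of baseline adjustment.** The documents give no correlation between baseline and follow-up BP, so the values here are assumptions. The SD becomes 10.53 × √(1 − r²):

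- r = 0.3: SD 10.05, power about 65%
- r = 0.5: SD 9.12, power about 73%
- r = 0.6: SD 8.42, power about 80%

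**The case against.** The strongest reply is that the documents do not say which SD is wrong. None of the three is derived, and they may come from different outside sources. If 8.3 is right, 2.2 mmHg and about 81% power stand, and the cohort cells are at fault. This holds. A reader might infer that the power is simply 61% rather than 80%, but the documents support only the conditional statement.

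A second reply is that the planned analysis is not the unadjusted comparison. Section 11.1 (Aim 1) includes the outcome's baseline value in the model, and Table 4 has systolic BP collected at baseline. This also holds: 61-62% is the figure without that gain. It does not explain the 8.3, because the row is labelled as a usual-care mean and SD and the two cohort cells take no credit for adjustment. A correlation of about 0.6 would be needed.

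Third, the 44/56 split is itself not firm. Aim 1 plans 350 patients per cohort with 90% and 85% retention, which gives 315 and 297.5, or 51% de novo. At that mix the SD is about 10.9 and the detectable difference about 2.85 mmHg at 229 per arm. The inconsistency grows, so this does not rescue the row, but it means 10.5 is tied to the footnote's split.

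Finally, the consequences are limited. A reader might infer that the trial is undersized, or that a null BP result will be misread. The sample size was set by the availability of 700 patients, no decision rule uses 2.2 mmHg, and the Exploratory Analyses paragraph also covers BP effects. A null result would ordinarily be judged from its own confidence interval.

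**Conclusion.** The inconsistency is real and does not depend on any outside figure: the three SDs in the systolic BP row cannot all be right at the footnote's cohort sizes. If the cohort SDs stand, the whole-sample SD is 10.4 to 10.5, the unadjusted detectable difference is about 2.7 to 2.8 mmHg instead of 2.2, and unadjusted power at 2.2 mmHg is about 61-62% instead of about 81%. These figures assume a two-sided 5% test, 229 per arm, the 44/56 split, and that the 80% stated for adherence also applies to this row, which the reproduction supports. Baseline adjustment would improve on them by an amount the documents do not allow one to fix.

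The point is confined to one non-primary outcome. It does not touch the trial's size or the power for adherence.

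**What to change.** Trace the three systolic BP SDs to their sources and make the row consistent.

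- If the cohort SDs stand, restate the total as SD about 10.5 with a detectable difference of about 2.8 mmHg, labelled as unadjusted and at the footnote's 44/56 split.
- If 8.3 stands, correct the cohort SDs and their detectable differences.
- If credit for baseline adjustment is wanted, state the assumed correlation and apply it to all three cells.

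The rest of the Total column merits a check at the same time. The eGFR-change row prints a total SD of 9.0, below both of its cohort SDs (11.0 and 15.0), and 9.0 at 305 per arm gives 2.0 rather than the printed 2.9.

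The cost is an edit to the table. If the cohort SDs stand, one stated figure becomes slightly less favourable. The design, the sample size and the planned analysis stay as they are, and no new estimator is needed.
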